5.1 Inclusion Criteria

Inclusion Criteria: Each participant must have a pre-treatment history that, when initially screened by a principal investigator or designee, documents that she/he meets all elements of the following:

1. Adult participants (aged 18 – 85 years inclusive).
2. Have been diagnosed with PD according to the UK Brain Bank Criteria (allowing for an exclusion in Step 2 for "more than one affected relative").
3. Participants must have demonstrated a sustained positive response to DRTs (e.g., levodopa, dopamine agonists or monoamine oxidase inhibitors) defined as either good or excellent responses (50-100%) for at least one year or moderate responses (30-49)% for at least three years prior to Screen.
4. Participant reports limitation or clinician-investigator determined limitation, based on knowledge of medical history, to one or more activities of daily living (e.g., writing, walking, bathing, dressing, eating, toileting, etc.).
5. Participants must be able and willing to consent to participate in the study for the RCT and OLE.
6. Participants must be willing and able to comply with study requirements.
7. Participants and investigators must expect that the participant will be able to remain on a stable regimen of concomitant therapies used for the management of PD motor and non-motor symptoms and not to introduce new medications used to treat motor or non-motor symptoms associated with PD during the RCT or the first three months of the OLE (Day197). Details are specified in the **Concomitant Medication** section below.
8. Participants must have at minimum a moderate burden of NMS (i.e., MDS-UPDRS part Ia and part Ib summed total score ≥ 9)⁵⁸ at study screen to avoid floor effects for the primary endpoint (MDS-NMS).
9. The principal investigator or designee must have confidence in the participant's ability to reliably use the TNM™ device, understand the assessments (provided in English only) and to complete the assessment battery within a given on-state period.
10. Must have a study partner (defined as someone who sees the participant for more than one hour a day, 3x per week) that is willing to consent and participate in the trial.
11. Participants must have capabilities to use and access smartphones for the collection of some study data and/or tablets or computers for access to telemedicine platforms.
**Study participants may be mechanically aided in data entry by study partners who have consented to take part in the study.
12. Must be willing to answer questions related to sexual interest, arousal and performance in an interview with study staff.

5.2 Exclusion Criteria

Exclusion Criteria: Each participant who meets any of the below will be excluded from study participation:

1. Participant anticipates being unable to attend all visits and complete all study activities in both the RCT and OLE.
2. Women of child-bearing potential who are pregnant or plan to become pregnant during the course of the RCT or OLE.
 - Women of child-bearing potential (i.e., are not yet either 3 years removed from their first menopausal symptom or 12 months removed from last menses), who are not abstinent or exclusively in same sex relationships must:
 - test negative for pregnancy as indicated by a negative urine pregnancy test;
 - agree to use an approved contraception method listed in section 5.3.3 for the entirety of the RCT and OLE;
3. Have a history or prior diagnosis of dementia or adjusted score ≤ 20 on the Montreal Cognitive Assessment (MoCA) at the screening visit.

**This exclusion criterion has been set specifically to improve the validity of scores assessed from the scaled questionnaires rather than reflecting a particular concern about safety for this population.

4. Have experienced a myocardial infarction, angina or stroke within the past 12 months or a transient ischemic attack (TIA) within 6 months.
5. Are receiving deep brain stimulation therapy.
6. Are treated with a pump for continuous delivery of dopamine replacement therapy.
7. Have received MRI guided high intensity focused ultrasound within the past 12 months.
8. Experience frequent falls (defined as 2 or more falls in the past month related to Parkinson's disease). Parkinson's falls are defined as falls associated with bradykinesia, freezing, turning, change in posture and postural dizziness and do not include accidental falls.
9. Work night shifts.
10. Has any significant co-morbidity or illness which in the opinion of the investigator would prevent safe participation in the study, compliance with protocol requirements or which presents with symptoms that are also common in PD.
11. Demonstrate suicidality at screening (scores ≥ 4 on the C-SSRS Baseline in section "Suicidal Ideation" (In the past Month)). Participants that respond affirmatively to question 4 or 5 (In the past Month) should receive a referral for mental health counseling according to local site regulations and standards.
12. Use a hearing aid that is implanted or that cannot be easily removed and replaced.
13. Have a cochlear implant or myringotomy tubes.

14. Have chronic tinnitus that has been ongoing for at least 3 months and causes significant impairment of communication and/or impairment of activities of daily living.
15. Have previously been diagnosed with traumatic brain injury with ongoing sequela.
16. Have been diagnosed with a co-morbid neurological disorder that may present with symptoms overlapping with PD (e.g., stroke, brain tumor, epilepsy, Alzheimer's disease, multiple sclerosis, amyotrophic lateral sclerosis, atypical Parkinsonism or aneurysm).
17. Have been previously diagnosed with either clinically meaningful central vestibular dysfunction (lifetime) or have experienced clinically meaningful peripheral vestibular dysfunction within the last 12 months. For this purpose, clinically meaningful is defined as vestibular dysfunction which causes at least a minimal impairment in the individual activities of daily living (e.g., dressing, bathing, preparing food, conducting household chores, work or recreational activities).
18. In the Investigator's opinion, currently abuse alcohol, abuse drugs (including legal, illegal or prescribed drugs) or have a history of alcohol or drug dependency within the past 5 years or use any drugs excluded as noted in the Excluded Medications List in section 5.3.2.
19. Have unresolved complications from a previous surgical procedure at the baseline visits, such as swelling or persistent pain, that requires medical intervention.
20. Have active ear infections, perforated tympanic membrane or labyrinthitis, as identified by a general ear examination performed by medically qualified Investigators.
21. Have a recent history of frequent ear infections (≥ 1 per year over the past two years).
22. Are currently enrolled or have participated in another interventional clinical trial within the last 30 days.
23. Has a planned surgery scheduled to occur during the RCT or the first 90 days of the OLE that would typically be followed with a prescription for pain management.
24. Have had eye surgery within the previous three months or ear surgery within the previous six months.

5.3 Concomitant Therapy

5.3.1 Approved Concomitant Medications

- The use of the following medications used to treat motor and non-motor symptoms associated with PD will be permitted during the study as long as the type or dose does not change during the course of the study or the 4 weeks immediately preceding the study: oral DRTs (e.g., levodopa/carbidopa or dopamine agonist based therapies), transdermal DRTs (e.g., rotigotine transdermal system), anti-cholinergics, MAO-B inhibitors, COMT inhibitors, amantadine, therapies to promote sleep including melatonin or benzodiazepines such as Klonopin, drugs to treat urinary frequency such as oxybutynin, tolterodine, trospium, solifenacin succinate, darifenacin, mirabegron, and fesoterodine fumarate.
- The use of selective serotonin reuptake inhibitors or other anti-depression/anti-anxiety medications will also be permitted during the study so long as the type or dose does not change during the study or the 12 weeks immediately preceding the study.

- Medications prescribed for other concomitant illnesses are allowed as long as they are not listed in the Excluded Medications list in section 5.3.2. Vaccines, supplements, and over the counter medications, including those taken occasionally (for example: seasonal allergy medications), should be documented if a dose occurred during the protocol timeframe.
- When medications are prescribed for indications other than symptoms associated with PD, physicians will be encouraged to utilize the one that is least likely to impact motor and non-motor symptoms associated with PD.
- Changes to medications for motor symptoms and NMS of PD are not permitted. Participants will be advised that during the RCT and first 3 months of the OLE, they should maintain patterns of usage of approved therapeutic medications that they normally use and that they should not initiate new medication (type, dosage or route of administration), medicating patterns or other interventions unless their provider deems the change to be medically necessary, as changes in concomitant treatments will interfere with the ability to attribute clinical change during the study to use of the Device. Any medically necessary changes to medications for motor symptoms and NMS of PD that do occur during the study will be recorded as concomitant medications and participants will continue in the study. Reasons for changes in medications used to treat motor symptoms or NMS of PD will be recorded, and participants who make changes in PD medications or add new medications likely to modulate symptoms associated with PD during the study will be included in the ITT analysis but excluded from the PP and mITT analysis.

5.3.2 Excluded concomitant medications, drugs and supplements

- Antipsychotic Medications (i.e., either neuroleptics or atypical antipsychotics)
- Anti-emetics (e.g., 5-HT3 receptor antagonists, D2 receptor antagonists, first-generation H1 Receptor antagonists, muscarinic antagonists, SP/NK1 receptors antagonists or corticosteroids that may be prescribed for anti-emetic purposes) prescribed chronically (taken more than 2 times per week, consistently)
- Inhaled or ingested cannabinoids (e.g., marijuana, cannabidiol (CBD), tetrahydrocannabinol (THC) or nabilone) within 4 weeks of screening.
- Any drug that has not been legalized on a United States Federal level
- Controlled substances that have not been prescribed under the care of a licensed-professional.
- Off-state rescue medications (e.g., apomorphine injections or levodopa-based inhalers) not prescribed with a stable dosing regimen (i.e. taken as needed/PRN).
- Mucuna pruriens supplements
- Medications producing side effects that mimic any of the motor or nonmotor symptoms of PD. For example, narcotic medications prescribed for pain management are known to produce several NMS evaluated as part of the primary outcome measure (e.g., cognitive impairments, constipation, etc.). Potential participants who are taking narcotics should have a 4-week washout from narcotic use prior to study screen. Questions regarding medication changes should be referred to the Medical Monitor

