4.1.1 STEM-PD RCT

Pre-screening procedures: Sites will recruit potential participants from their practice/service or the general public as long as inclusion/exclusion criteria can be verified. The use of advertisements may be used at the site's discretion. During the pre-screening period, the study should be described, preliminary questions answered, and review of potential participant's medical records can occur, however, no protocol-specific activities should occur until after informed consent is obtained and documented.

Study screening procedures (Day –14 to –1):

Informed Consent

Participants will be shown an example of the Study Device as part of the informed consent process. Potential participants should be given a private space to review the ICF and an ample opportunity to have all questions answered. Capacity to provide consent must be assessed by a clinician with experience working with Parkinson's Disease patients, and should be documented, as no Legally Authorized Representative is allowed. Informed consent should be signed and dated by both the study participant and authorized study staff performing the informed consent process, and a signed and dated copy provided to the participant, prior to any study related activities being conducted. Although participants will only consent at the screen for involvement in the 16-week (112 days) STEM-PD RCT portion of the study, screening applicants who do not anticipate participating in the 36-week (252 days) OLE will be excluded from the study.

Additionally, the protocol-required study partner will also be provided with an informed consent to review and discuss. The purpose of the informed consent for the study partner is to ensure that they understand and agree that they are required to assist, if necessary, the participant in the execution of certain at home assessments, such as the TUG, as well as answer specific questions by the study staff related to the participant's overall health and activities of daily living. The study partner should be afforded the same informed consent process stipulations as the participant, including that the informed consent be signed and dated by both the study partner and the authorized research study staff performing the informed consent process, and provided a sign and dated copy.

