8.1 Device Deficiency

A device deficiency is an inadequacy of a medical device related to its identity, quality, durability, reliability, safety, or performance, such as malfunction, misuse or use error and inadequate labeling.

All device deficiencies will be documented, and the device will be returned to the device manufacturer for analysis, if possible. Device deficiencies are NOT to be reported as AEs. However, if there is an AE that results from a device deficiency, that specific event would be recorded on the appropriate CRF.

8.2 Adverse Events (AEs), Adverse Device Effects (ADEs), Serious AEs (SAEs), Serious Adverse Device Effects (SADEs), Unanticipated Adverse Device Effects (UADE) and Unanticipated Problem Reporting

8.2.1 AEs, ADEs, SAEs, SADEs and UADEs will be defined per ISO14155:2020 and/or 21 CFR Part 812, as described below.8.2.1 Adverse Event (AE):

An AE is any untoward medical occurrence, unintended disease or injury, or untoward clinical signs (including abnormal laboratory findings) in participants, users, or other persons, whether or not related to the investigational medical device. This definition includes events related to the investigational medical device and the events related to the procedures involved. For users and other persons, this definition is restricted to events related to the investigational device. AEs will be collected starting from the time the participant signs informed consent until the follow-up period is completed.

8.2.2 Adverse Device Effect (ADE):

An Adverse Device Effect (ADE) is an AE related to the use of an investigational medical device. This definition includes AEs resulting from insufficient or inadequate instructions for use, deployment, implantation, installation, or operation, or any malfunction of the investigational medical device. This definition includes any event resulting from use error or from intentional misuse of the investigational medical device.

Traditional, diagnostic CVS has been used for roughly a century, and there are no reports in literature of significant adverse events.

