8.2.6.1 Documentation and assessment

- Following the informed consent process, clinical study participants will be routinely questioned about AEs at all visits from the clinical research staff. All AEs, regardless of treatment group or suspected causal relationship to the investigational device, will be recorded in the participants' source documentation.
- For all AEs, sufficient information will be obtained as to 1) determine the severity of the event; 2) assess the casual relationship between the adverse event and the investigational device; and 3) determine the outcome of the event.
- AEs will be followed until the event (or its sequelae) resolves or stabilizes at a level acceptable to the investigator and sponsor.

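### The narcotics rule in Protocol 5.3.2 can be read as prompting current users to stop a prescribed analgesic before they have consented

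*Protocol*

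**What the plan says.** Section 5.3.2 of the protocol lists excluded medications. Its last bullet covers drugs whose side effects resemble PD symptoms, with narcotics as the example. It then states: "Potential participants who are taking narcotics should have a 4-week washout from narcotic use prior to study screen". The bullet ends: "Questions regarding medication changes should be referred to the Medical Monitor".

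The list acts on eligibility through exclusion criterion 18 in 5.2, which rules out people who "use any drugs excluded as noted in the Excluded Medications List in section 5.3.2".

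Section 4.1.1 places informed consent within screening (Day -14 to Day -1), and the RCT schedule of events marks it at the Screen visit only. Pre-screening may include describing the study, answering preliminary questions and reviewing records, but "no protocol-specific activities should occur until after informed consent is obtained and documented". The informed consent paragraph repeats the rule: signatures come "prior to any study related activities being conducted".

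On safety capture, 8.2.1 states: "AEs will be collected starting from the time the participant signs informed consent until the follow-up period is completed". Section 8.2.6.1 likewise starts adverse event questioning after consent: "Following the informed consent process, clinical study participants will be routinely questioned about AEs at all visits".

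Section 5.4 allows a screen failure to be rescreened once the reason for exclusion has gone, with at least 30 days between eligibility assessments.

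**The concern.** The narcotics sentence is about people who are taking the drug now, and it puts the washout ahead of the visit at which consent is first signed. A coordinator who finds an opioid prescription during permitted record review could take it to mean that the patient should come off the drug for four weeks and then be screened. That is a realistic setting, because 5.5 expects most participants to come from the sites' existing patients after record review.

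If that happened, someone would give up a prescribed analgesic in order to enter a trial they had not yet agreed to join. Any resulting harm, such as uncontrolled pain or withdrawal symptoms, would occur before adverse event collection begins, although ordinary care might continue. What is at stake is the order of consent and the protection of a few individuals, not the trial's statistical conclusions.

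**Working it through.** The plan states no figure on this point, so the check is a comparison of texts plus day counts.

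**Inputs**
- Washout: 4 weeks = 4 × 7 = 28 days, before the screen (5.3.2).
- Screening window: Day -14 to Day -1, with first consent at the screen (4.1.1, schedule of events).
- Adverse event collection: from signed consent (8.2.1).
- Minimum interval before rescreening: 30 days (5.4).

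**Where a study-prompted washout would fall on a first screen**

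Latest start = screen day − 28.
- Screen on Day -14: −14 − 28 = Day -42.
- Screen on Day -1: −1 − 28 = Day -29.

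The washout ends before the screen and consent is signed at the screen, so none of the 28 days follows consent. This count follows directly from reading the sentence as an instruction to current users. It is not independent evidence for that reading.

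**Which reading the text supports**

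| Wording | Points towards |
|---|---|
| 5.3.2 narcotics: addressed to current users, who should have a washout | Stopping the drug for study entry |
| 5.3.2 cannabinoids: "Inhaled or ingested cannabinoids (e.g., marijuana, cannabidiol (CBD), tetrahydrocannabinol (THC) or nabilone) within 4 weeks of screening" | Look-back; shows that such wording was available and that the list uses it |
| 5.3.1: PD drugs stable for the preceding 4 weeks, antidepressants for 12 weeks | Look-back |
| 4.1.1 and the schedule of events: no washout step | Look-back; no one is assigned to direct a withdrawal |
| 5.3.2: medication-change questions go to the Medical Monitor | Neutral; it may concern the washout or changes during the study |

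The wording of the sentence leans one way and its surroundings lean the other. The protocol does not settle which is meant.

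**Whether a compliant route exists**

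Suppose a current user consents, fails screening, and takes the last dose *t* days after that consent. The earliest rescreen that respects both rules is max(30, *t* + 28) days after the first consent. The protocol gives no *t*. Over an assumed range:
- *t* = 0: max(30, 28) = 30 days
- *t* = 7: max(30, 35) = 35 days
- *t* = 14: max(30, 42) = 42 days

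So 5.4 can accommodate a 28-day washout after consent, with 30 − 28 = 2 days to spare at *t* = 0. Section 5.3.2 does not point to this route.

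**The case against.** The strongest reply is that 5.3.2 is an exclusion list, not a procedure. It tells no one to stop, taper or supervise a narcotic, and no washout appears among the pre-screening steps, the screening steps or the scheduled events. The other pre-study drug windows in 5.3 are look-backs, and the cannabinoid rule has the same 4-week length. Section 4.1.1 states the consent rule twice. A site reading both sections has a compliant course: direct no withdrawal before consent, treat a current user as ineligible for now, and use 5.4 later if the person has stopped. Events before consent go uncollected for every participant, not only for narcotic users.

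Most of this stands. A reader might infer that the protocol requires or authorises withdrawal before consent, or that a site cannot follow 5.3.2 without breaching 4.1.1. The documents do not support either inference. Both need the added premise that the site directs the withdrawal, which 5.3.2 does not say. People who stopped earlier for clinical reasons raise no conflict at all.

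What the reply does not remove is the wording. A washout for people who are taking the drug is an odd way to express a look-back. The Medical Monitor sentence covers questions only; it neither requires consent nor starts adverse event collection. The rescreen route is optional and is not linked to the washout.

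**Conclusion.** The point holds as a minor ambiguity about the order of consent and washout. The narcotics sentence has a plausible benign reading as an eligibility look-back. It also has a reading, open on its face, in which a current user is prompted to stop a prescribed analgesic before consent. Under that second reading the whole 28-day washout on a first screen precedes both consent and adverse event collection.

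This rests on two assumptions: that the person is using a narcotic when identified, and that stopping is prompted by the study rather than by clinical need. The documents do not say how many of the up to 290 people screened would fit that description, and it may be none.

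A reader might also infer an effect on the trial's results. There is none: no endpoint, power calculation or analysis depends on this sentence.

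**What to change.** In 5.3.2, replace the narcotics sentence with a look-back in the style of the cannabinoid bullet, so that the excluded item is *narcotic use within 4 weeks of screening*. Because a look-back alone leaves the incentive to stop, add: *Sites must not ask or advise anyone to stop a narcotic for study entry before informed consent; a current user who later stops may be rescreened under 5.4.* Keep the Medical Monitor referral. Whether and how a narcotic is stopped remains a clinical decision.

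The cost is two sentences. Anyone who consents first and then rescreens waits at least 30 days, and longer if the last dose comes more than 2 days after consent. The study visit schedule does not change. The sponsor may choose to require adverse event collection between screen failure and rescreen, but that adds burden and the fix does not depend on it.
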